7.3 Biospecimen Evaluations

Pre- and post-vaccination whole blood samples will be processed to isolate serum, peripheral blood mononuclear cells (PBMCs), RNA, and DNA. Specimens will be processed at the Neutrophil Monitoring Laboratory (NML), LCIM, and the Laboratory of Virology at the Rocky Mountain Laboratories at NIAID, the Department of Laboratory Medicine (DLM) at NIH, and the Section on Immunoengineering (IE) at the National Institute of Biomedical Imaging and Bioengineering (NIBIB). The saliva testing for SARS-CoV-2 using PCR will be performed in the DLM under an EUA.

Sample types, volumes, and laboratory evaluations are provided in section 1.2. For pediatric subjects, blood volume limitations may preclude execution of all the tests required. In such cases, the PI will prioritize which tests will be performed.

7.3.1 Samples for Genetic/Genomic Analysis

Targeted genetic analyses may include high throughput sequencing of T- and B-cell receptor repertoires, human leukocyte antigen (HLA) typing, and single nucleotide polymorphism (SNP) chips. This study will not involve genetic tests intended to discover disease-determining genes, but will only involve amplification of rearranged TCR immunoglobulin heavy chain (IGHC) gene segments. It is possible that the investigators might refer interested participants and their families to the Centralized Sequencing Initiative protocol (17-I-0122). If a participant chooses to co-enroll on this protocol and 17-I-0122, we will have access to the identified findings from whole genome/exome sequencing via the Genomic Research Information System platform for use in this study to confirm a known genetic mutation or update information about a participant's immune status if an unknown but clinically significant mutation is discovered. The informed consent document will address the sharing of data between studies, and no additional samples outside of those required of each protocol will be obtained.

If a saliva sample is found to be positive for SARS-CoV-2, the virus will be isolated from the sample for genomic profiling. The viral genetic sequences will be deposited into GenBank, along with donor participant information that includes age category, sex, and whether the donor is immune compromised. No human genetic information will be shared in this process, as the goal is sequencing of the virus and any human data will be filtered out.

7.4 Plan for the Return of Results

Analyses under this protocol may identify results or incidental findings that are relevant to the health or medical care of subjects (either affected participants or healthy controls). Results of clinical laboratory assessments performed on this study (ie, CBC w/differential) will be returned

to participants, as will results of the SARS-CoV-2 PCR tests. All other laboratory assays, including the SARS-CoV-2 antibody tests, are for research only, and a result would only be returned if confirmatory testing in a laboratory certified by the Clinical Laboratory Improvement Amendments (CLIA) is available. If needed, the study team will contact the subject and request a sample for confirmatory testing or recommend other laboratories where they can go for testing. After confirmation, the principal investigator or designee will contact the subject to inform them of the finding and counsel them on the result. The study team may also provide consultation with a subject's healthcare provider based on the result.

8 STATISTICAL CONSIDERATIONS

8.1 Study Hypotheses

This is an exploratory study to characterize the immune response and vaccine-associated AEs in individuals with a variety of immune disorders who receive COVID-19 vaccination, in addition to describing disease prevalence and severity among subjects previously infected with SARS-CoV-2 and whether this affects vaccine immune response. We therefore hope to generate and test a number of hypotheses, including but not limited to:

1. Assessing whether and which of the immune correlates measured for the primary, secondary and exploratory endpoints change significantly after vaccination from baseline, comparing the response among various immune deficiency/dysregulation conditions and healthy volunteers (longitudinal change in immune response).
2. Assessing whether and which of the immune correlates measured for the primary, secondary, and exploratory end-points are significantly different among various immune disorder subgroups and healthy volunteers (cross-sectional immune response).
3. Assessing whether the dose 1 antibody response is correlated with the dose 2 antibody response among various immune disorder subgroups and healthy volunteers.
4. Assessing the incidence of vaccine-associated AEs among various immune disorder subgroups and healthy volunteers.
5. Assessing the prevalence and severity of COVID-19 symptoms among various immune disorder subgroups and healthy volunteers.

8.2 Patient Populations for Analysis

The numbers provided for each group are an estimated number to be enrolled for each immune deficiency/dysregulation sub-group:

1. Combined immunodeficiencies (n=50)
2. Predominantly antibody deficiencies (n=40)
3. Disorders of immune regulation (n=40-60)
4. Congenital defects of phagocyte number or function (n=40-60)
5. Defects of intrinsic and innate immunity (n=25-30)
6. Autoinflammatory disorders (n=20)
7. Complement deficiencies (n=5-10)
8. Bone marrow failure syndrome (n=5-10)

9. Subjects with inborn errors of immunity who have received hematopoietic stem cell transplantation or gene therapy (n=20-30)
10. Subjects with secondary immunodeficiencies, to include those who have received hematopoietic stem cell transplantation or gene therapy (n=30-50)
11. Healthy volunteers (n=120 [2:1 healthy to largest immunodeficiency group])

Healthy volunteers will be enrolled to be representative of binned-age groups and sex distribution of the immune deficient study population. Age bins will be (3-5], (5-12], (12-16], (16-25], (25-45], (45-65], and 65+.

8.3 Sample Size Justification

The sample sizes proposed in this protocol were set based on the primary objectives of this study, which are to characterize the immune response to COVID-19 vaccination as measured by enzyme-linked immunosorbent assay (ELISA) anti-S-2P and anti-RBD IgG titers at approximately 3-4 weeks following each vaccination and in long-term follow-up. The following sample size determination is based on results of the phase 1 dose escalation study of the Moderna mRNA vaccine.⁹ Fifteen participants received a dose of 100 ug of vaccine, and the means and standard errors of the log₁₀ antibody titers at the nearest timepoints to the times at which we propose to collect samples are summarized in the table below.

Target	Study day	Mean log ₁₀ -titer (Standard error)
S-2P	29	5.04 (0.28)
	56	5.89 (0.19)
RBD	29	4.97 (0.38)
	56	5.57 (0.27)

We assume that healthy volunteers in the upcoming trial have similar immune responses to those reported in the Moderna Phase I trial, and that immune deficiency/dysregulation shifts the log₁₀-titer distribution among individuals with immune deficiency/dysregulation but does not change the standard deviation of the responses. We also suppose that healthy volunteers and immune deficient/dysregulated individuals have similar baseline distributions, which is reasonable as both groups are naïve at baseline. As we were unable to obtain specific estimates of antibody responses to the Pfizer vaccine that could be used to estimate the sample size for this study, we are left to assume that responses to the Pfizer vaccine are similar to the Moderna vaccine.

Using the estimates from the Moderna study, we calculate, and plot below, the smallest differences in mean log-titers that we would be able to detect using a two-sided two-sample t-test with either 80% or 90% power while controlling the type I error rate at $\alpha=0.05$ as a function of sample size. We also display the widths of 95% confidence intervals for a difference in mean log-titers. As an example, a sample size of 20 immune deficient/dysregulated individuals and 20

healthy volunteers should be sufficient to detect a true difference in mean anti-RBD log-titer of 0.4 at day 29 with 90% power, or a true difference of 0.35 with 80% power, while controlling the type I error rate at $\alpha=0.05$. We would also expect the width of a 95% confidence interval for the difference in mean log- titers to be approximately 0.35 units. It is also useful to consider the minimum detectable standardized effect size, also shown below, as antibody responses to other vaccines may differ from responses to the Moderna vaccine. Continuing with our example, a sample size of 20 participants per arm would be sufficient to detect a 1.05 standard deviation difference with 90% power using a two-sided two-sample t-test while controlling the type I error rate at $\alpha=0.05$.

[figure not shown]

Figure 2. Sample size estimates for primary endpoint. **A)** Lines represent number of participations required in each group and the smallest detectable differences in mean log-titers using a two-sided two-sample t-test with either 80% or 90% power while controlling the type I error rate at $\alpha=0.05$. **B)** Widths of 95% confidence intervals for a difference in mean log-titers. **C)** Number of participants required in each group to detect differences in standardized antibody effect size using a two-sided two-sample t-test with either 80% or 90% power while controlling the type I error rate at $\alpha=0.05$.

While it is hard to generalize antibody responses across the many immune conditions in this study given the phenotypic heterogeneity between and within diseases, patients in the following groups would generally be expected to have poor antibody responses to vaccination:

- Defects of cellular and humoral immunity (n=20) (e.g. RAG, DOCK8, adenosine deaminase [ADA], nuclear factor-kappa B essential modulator [NEMO])
- Predominantly antibody deficiencies (n=40) (e.g. X-linked agammaglobulinemia [XLA], CVID, activated PI3K delta syndrome 1/2 [APDS1/2], Ras-related C3 botulinum toxin substrate 2 [RAC2], caspase recruitment domain-containing protein 11 [CARD11], gain-of-function [GOF])

Hence, we expect to have adequate power to resolve differences in mean antibody responses between patients in these immune deficiency groups and healthy controls. Vaccine responses from other disease groups can be variable,¹⁰⁻¹² but most would be expected to respond to vaccination. We would like to be able to detect at least a one standard deviation difference in mean log-titer for those immune deficient/dysregulated groups where we do not have prior information to inform our expectations about the magnitude of the difference vis-a-vis healthy controls. Therefore, the proposed sample sizes should suffice.

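### Section 8.3 says the sample sizes suffice for a one-SD difference from healthy controls, but a group of 5-8 has only 58-78% power; the Section 8.2 totals also differ from the synopsis

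*Combined protocol and SAP*

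**What the plan says.** Section 8.3 sets its target for groups without prior information in these words: "We would like to be able to detect at least a one standard deviation difference in mean log-titer". It limits this to groups "where we do not have prior information to inform our expectations about the magnitude of the difference vis-a-vis healthy controls". It then concludes, with no exception for small groups: "Therefore, the proposed sample sizes should suffice".

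The method in the same section is a "two-sided two-sample t-test with either 80% or 90% power" at alpha 0.05. It assumes that immune deficiency shifts the log-titer distribution but "does not change the standard deviation of the responses". The only worked example on the standardized scale is that "a sample size of 20 participants per arm would be sufficient to detect a 1.05 standard deviation difference with 90% power".

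The planned sizes are in Section 8.2, where they are described as estimated enrolment. Two of the ten affected groups are very small: "Bone marrow failure syndrome (n=5-10") and "Complement deficiencies (n=5-10"). The other eight are planned at 20 or more. Healthy volunteers are set at 120, twice the largest affected group. The synopsis (Section 1.1) instead gives 400 affected and 100 healthy participants, 500 in all, with an accrual ceiling of 600.

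**The concern.** The worked example has 20 participants per arm, but the conclusion covers every group, including those planned at 5-10. In a two-sample comparison the smaller arm governs precision, so a large control group cannot make up for it. The sentence therefore gives a group of 5 the same assurance as a group of 20 or more.

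This matters because Section 8.1 plans to test which immune measures differ significantly between disorder subgroups and healthy volunteers. With 5 evaluable participants a true one-SD deficit would be missed about 42% of the time, and with 7 about 28%. A reader who relies on the sufficiency statement could take a non-significant result in such a group as evidence of a normal vaccine response.

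The second issue is that the plan carries two sets of enrolment totals, which leaves the intended size of the study unclear.

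**Working it through.** **Inputs.** Two-sided two-sample t-test, alpha 0.05, equal SDs, power levels 80% and 90% (Section 8.3). Target d = 1 SD (Section 8.3). Affected group of 5-10 (Section 8.2). Controls: 120 (Section 8.2) or 100 (synopsis).

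**Formula.** Power is the probability that a noncentral t variable with n1 + n2 − 2 degrees of freedom and noncentrality d / √(1/n1 + 1/n2) exceeds the two-sided 5% critical value.

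**Reproducing the plan's figure.** For 20 v 20 and d = 1.05: noncentrality 1.05 / √(1/20 + 1/20) = 3.32, 38 degrees of freedom, critical value 2.024, power 89.9%. The plan states 90%, so the method matches.

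**Applying it to the small groups.** For 5 v 120 and d = 1: noncentrality 1 / √(1/5 + 1/120) = 2.19, 123 degrees of freedom, critical value 1.979, power 58.5%. The other sizes follow in the same way:

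| Evaluable n | Power at 1 SD v 120 | Power at 1 SD v 100 | Detectable at 80% power v 120 (SD) |
|---|---|---|---|
| 5 | 58.5% | 58.0% | 1.289 |
| 6 | 66.0% | 65.4% | 1.181 |
| 7 | 72.3% | 71.7% | 1.098 |
| 8 | 77.6% | 76.9% | 1.031 |
| 9 | 81.9% | 81.3% | 0.976 |
| 10 | 85.4% | 84.8% | 0.929 |
| 20 | 98.4% | 98.2% | 0.681 |

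A simulation of 100,000 runs against 120 controls agrees: 58.7% at n=5, 77.6% at n=8 and 85.4% at n=10. The smallest group that reaches 80% is 9, and 90% needs 12, with either control total. So four of the six sizes in the 5-10 range miss 80%, and all six miss 90%. The 95% confidence interval half-width against 120 controls is 0.90 SD at n=5 and 0.65 SD at n=10.

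**Would more controls help?** Hardly. Even 10,000 controls would give 61% at n=5 and 75% at n=7.

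**Sensitivity to non-evaluable participants.** The plan gives no rate, so 20% and 30% in both arms are assumed:

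- 10 v 120 becomes 8 v 96 (76.8%) or 7 v 84 (71.0%).
- 20 v 100 becomes 16 v 80 (95.1%) or 14 v 70 (92.2%).

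**Totals.** In the order of Section 8.2:

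- Affected, low end: 50+40+40+40+25+20+5+5+20+30 = 275.
- Affected, high end: 50+40+60+60+30+20+10+10+30+50 = 360.
- With 120 healthy volunteers: 395-480 overall.

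Against the synopsis, the affected total is 40-125 short of 400, healthy volunteers are 120 rather than 100, and the overall total is 395-480 rather than 500.

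**The case against.** - **Scope.** The study is exploratory, the sizes are labelled as estimates, and the sentence is true for eight of the ten affected groups. This stands, and it confines the point to one or two groups. It does not make the sentence true for them.
- **Power level.** The sentence names no power level, and 9 or 10 evaluable participants do meet 80%. The fair range for 5-10 is 58-85%. That still leaves most of the planned range short of the lower level.
- **Prior information.** Section 2.2 expects people with complement defects to have B- and T-cell levels close to those of healthy volunteers, so that group may fall outside the target. Bone marrow failure syndrome has no such statement and is not among the expected poor responders listed in Section 8.3.
- **More efficient analysis.** Section 8.4.1 says the t-test calculation is probably slightly conservative relative to the repeated-measures model. The variance reduction needed for 80% power at one SD against 120 controls is 1 − 1/(detectable SD)²: 6% at n=8, but 17% at n=7, 28% at n=6 and 40% at n=5. A slight gain could cover n=8, not the rest. The optional Bayesian model in Section 8.4.1 could help, but its gain is not quantified.
- **Evaluability.** The waiver of earlier samples in Sections 1.2 and 4.1 applies to people who enrol after vaccination without a planned booster or stored samples. Out-of-window samples may still be used, and home microsamplers provide antibody titers. General loss may therefore be modest. Still, Section 8.4.1 expects missing data, and the shortfall at 5-8 needs no loss at all.
- **Figure 2.** It may show what small groups can detect. Its image is missing from the copy reviewed, so the point concerns the sentence and not the plotted curves.

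**Conclusion.** The concern holds. Over most of the planned 5-10 range, the unqualified sufficiency statement fails on Section 8.3's own test and assumptions: power for one SD is 58-78% at 5-8 evaluable participants against 120 controls (58-77% against 100), and reaches 82-85% only at 9-10 (81-85% against 100). It applies firmly to bone marrow failure syndrome and arguably to complement deficiencies. Groups of 20 or more meet the target comfortably.

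The figures assume equal SDs and unadjusted alpha 0.05, and they count evaluable rather than enrolled participants.

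The difference in totals is also real. The estimates fit under the ceiling of 600, but neither that nor their label explains why even the upper affected total, 360, is below 400, or why there are 120 healthy volunteers rather than 100. The effect on power of 100 rather than 120 controls is less than one percentage point, so this second point is one of clarity. Both should be corrected.

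**What to change.** Qualify the sufficiency sentence in Section 8.3, for example:

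> Assuming equal SDs and counting evaluable participants, groups of 20 or more have about 98% power or higher to detect a one-SD difference from 100-120 healthy controls (about 92-95% for 20 v 100 if 20-30% of both arms are not evaluable, an assumed range). For groups of 5-10, the difference detectable with 80% power against 120 controls runs from about 1.29 SD (n=5) to 0.93 SD (n=10). Results in these groups are reported as estimates with 95% confidence intervals, and non-significance is not read as a normal response.

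Separately, reconcile the planned totals in Section 8.2 (275-360 affected, 120 healthy) with the synopsis (400 and 100), or explain the difference.

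The cost is protocol wording only, with no extra participants. The stated sensitivity becomes less favourable for the one or two groups of 5-10.

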8.4 Statistical Analysis

Multiple sets of analyses will be done to characterize the immune response in each of the groups of participants with immune deficiency/dysregulation:

1. Within-group: Estimate the vaccine response at each timepoint relative to baseline within an immune deficiency/dysregulation group.
2. Longitudinal between-groups: Compare the vaccine response profiles of different groups at sampling times.
3. Adjusted analyses controlling for SARS-CoV-2 infection.

For symptoms: focus will be on estimation of the proportion of symptoms that are present or absent in these individuals. Variables will be presented by frequency distribution (e.g. frequency counts, percentages, and 95% confidence intervals). In addition, this study will be used as the basis for hypothesis generation to explore disease manifestations in individuals with different types of immune deficiency/dysregulation if the number of enrolled individuals allow.

8.4.1 Analysis of the Primary Endpoint

Log transformed antibody measurements will be modeled within a mixed model repeated measures (MMRM) framework, which is a longitudinal mixed model with fixed effects for (categorical) timepoint, immune deficiency/dysregulation, and the interactions of timepoint with immune deficiency/dysregulation and timepoint with baseline measurement, along with possible adjustment other covariates, such as age and sex. In this framework, we also include correlated subject-level random effects for each timepoint to account for clustered data. This also allows us to estimate the correlation between antibody responses to the first and second doses of vaccine. MMRM models are an appropriate tool for assessing response profiles in longitudinal studies where missing data is expected and it is appropriate to assume that data are missing at random conditional on observable covariates.^{13,14} The previous sample size justifications based on two-sample t-tests are likely to be slightly conservative as we expect the MMRM framework to make more efficient use of the data. Models will either be fit using the 'nlme' package in R, or, if a Bayesian formulation is deemed to be preferable for the purpose of incorporating prior information, can be fit using the 'brms' and 'rstanarm' packages.

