There is some literature regarding the immune response in individuals with inborn errors of immunity to vaccination, including inactivated or subcomponent vaccines like the influenza or *Haemophilus influenzae* type b vaccines,^{5,6} and live-attenuated vaccines such as the measles-mumps-rubella and varicella vaccines.⁷ Depending on the immunologic defect, vaccine immunogenicity can vary widely, leaving some immunodeficient individuals inadequately protected. For example, individuals with complement defects should produce B- and T-cells in levels relatively similar to that of healthy volunteers, while others, like those with Wiskott-

Aldrich Syndrome, produce antibodies but a weak or absent T-cell response, and those with common variable immunodeficiency are only capable of producing T-cells without antibody. Because of this complexity, it is necessary to obtain a comprehensive understanding of the immunologic response to vaccines to better understand both the level of cellular and humoral protection against COVID-19 and also their estimated contribution to herd immunity.

Unfortunately, individuals with immunodeficiencies are typically excluded from vaccine trials measuring immunogenicity and safety, as was the case for the COVID-19 vaccines currently authorized or approved for use in the United States. This creates a need to study AEs in immunodeficient people to determine the safety and tolerability of the COVID-19 vaccines, especially in light of concerning anaphylaxis episodes in a minority of people who were vaccinated against COVID-19,⁸ even though AEs in this group, specifically in individuals with impaired T-cell responses, are usually limited to live vaccines.

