Participants who are able to come to the NIH will have the additional option to provide blood samples at days 1 and 3 after each vaccination in order to capture immediate vaccine-induced perturbations of immune responses. Samples will be used to study short-term immunological effects of immunization and boosting. If additional booster doses are received, participants will be asked to submit optional blood samples 21-28 days after the booster vaccination(s), through the 5th dose of a COVID-19 vaccine. Samples received outside of that window samples received outside of the requested windows are acceptable and will be analyzed at the discretion of the PI. Additional optional blood samples may be provided at approximately 6, 12, and 24 months after the final vaccination to assess long-term immunological persistence of vaccine-derived antibodies and T-cell responses. Research evaluations on these samples will include baseline and post-vaccine autoantibody levels as well as SARS-CoV-2 antibody titers to the S, N, and RBD proteins. Serology has been validated across fresh serum and dried blood samples collected using microsamplers (see Figure below)⁸. Venous blood draw may be waived if a participant is unable to obtain it at any given timepoint.

[figure not shown]

Figure 1. Quantification of antibody concentration utilizing 4PL sigmoidal model of recombinant antibody spiked into seronegative blood. **A)** Anti-RBD recombinant human antibody (IgG and IgM) was added to whole blood from two seronegative donors, then absorbed to microsamplers and remaining blood was spun down to isolate serum and analyzed on full spike ectodomain trimer (spike) or receptor-binding domain (RBD) ELISA. Data are mean \pm SEM, n = 3, red = microsampler eluate, gray = matched serum. **B)** Direct comparison of absorbance of range of recombinant antibody concentration in serum (y axis) versus microsampler (x axis) blood samples. **C)** Sigmoidal four-parameter logistic (4PL) curve fitting to recombinant antibody dilution series, 95% confidence intervals shown shaded around fit curve, n = 12 replicates per data point, red = Spike IgG, orange = RBD IgG, blue = Spike IgM, purple = RBD IgM. **D)** Quantification of IgG levels in a sample high-incidence population. **E)** Upper limit of quantification at 1:400 dilution of serum into ELISA (1:10 dilution of microsampler eluate), n = 68. From ref⁸

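### Section 8.4.1 fits every log titer in a Gaussian mixed model with no rule for values outside the ELISA range, although values below the floor are foreseeable and can distort the patient-healthy difference

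*Combined protocol and SAP*

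**What the plan says.** The primary endpoint is the change in S and RBD IgG titer from baseline, measured after each dose. Section 8.3 gives the measure as "enzyme-linked immunosorbent assay (ELISA) anti-S-2P and anti-RBD IgG titers". For the analysis, section 8.4.1 states: "Log transformed antibody measurements will be modeled within a mixed model repeated measures (MMRM) framework". The fixed effects include timepoint by group and timepoint by baseline. On software it says "Models will either be fit using the 'nlme' package in R", with brms or rstanarm as the alternative "if a Bayesian formulation is deemed to be preferable for the purpose of incorporating prior information". Censoring is not given as a reason for that choice. The text contains no numeric assay limit, no rule for values outside the range, no re-dilution step and no responder-type analysis.

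Three other places bear on whether such values will occur:

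- **Floor after vaccination.** Section 2.2 says "those with common variable immunodeficiency are only capable of producing T-cells without antibody". Section 8.3 expects poor antibody responses in two groups, planned there at 20 and 40 participants (60 in all). The group of 40 includes common variable immunodeficiency.
- **Floor at baseline.** Section 8.3 says "We also suppose that healthy volunteers and immune deficient/dysregulated individuals have similar baseline distributions", on the ground that both groups are naive.
- **Ceiling.** The legend to Figure 1 in section 4.1 reads "Upper limit of quantification at 1:400 dilution of serum into ELISA (1:10 dilution of microsampler eluate), n = 68". No value is given in the text.

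**The concern.** A Gaussian mixed model fitted in the ordinary way takes each recorded value as an exact log titer. A titer below the lower limit is known only to lie below it. If it is recorded at the limit, the group mean moves toward the limit and the group SD falls. The share affected will differ by group, because the groups were chosen for their different capacity to make antibody. The distortion therefore does not cancel in the patient-healthy contrast.

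Section 8.3 assumes that immune deficiency shifts the distribution and leaves the SD unchanged. Recorded values that pile up at a limit cannot meet that assumption.

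Baseline matters too. If naive baselines fall below the limit, the baseline covariate is largely a substituted constant. The within-group change from baseline, which section 8.4 lists first, then moves with the constant chosen: the limit and half the limit differ by log10(2) = 0.30.

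The missing-at-random argument in section 8.4.1 does not cover this. Whether a titer is out of range depends on the titer itself. What is at stake is the estimated size of the difference and its interval, which are the main product of a study meant to characterize response.

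**Working it through.** **The plan's own figure.** Section 8.3 says 20 against 20 detects a 0.4 log10 anti-RBD difference at day 29 with 90% power, and 0.35 with 80%, by a two-sided t-test at 0.05. With 0.38 used as the SD, noncentral-t power is 0.900 for 0.40 and 0.810 for 0.35. The figure reproduces. The table labels 0.38 a standard error, but the stated power requires it to be the SD, so it is used that way here.

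**Inputs.** From the documents: SD 0.38 in both groups and healthy mean 4.97 (section 8.3, anti-RBD day 29); 120 healthy volunteers and 40 with predominantly antibody deficiencies (section 8.2). Assumed, because the documents give nothing: a true difference of -1.00, and 25% or 50% of patients below the floor.

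**Floor only, values recorded at the limit.** Let p be the share of patients below the floor, z = Φ⁻¹(p) and σ = 0.38.

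- Upward shift of the patient mean: σ[φ(z) + zp].
  - p = 0.25: 0.38 × (0.3178 − 0.6745 × 0.25) = 0.057, so the estimate is −1.00 + 0.057 = −0.94.
  - p = 0.50: 0.38 × 0.3989 = 0.152, so the estimate is −0.85.
- Variance of the recorded patient values: σ²[z²p + (1 − p) + zφ(z) − (φ(z) + zp)²]. This is 0.627σ² at 25% (SD 0.301) and 0.341σ² at 50% (SD 0.222).
- Standard error of the difference: √(0.38²/120 + SD²/40) = 0.059 at 25% and 0.049 at 50%. The bias is therefore 0.057/0.059 = 0.96 and 0.152/0.049 = 3.1 standard errors.
- Coverage of the nominal 95% interval is about 84% and 13% by the normal approximation. Simulation of the t-interval with separate group variances gives 85% and 11%.
- With one common variance the interval is wider. At 50% the pooled variance is (119 × 0.1444 + 39 × 0.0492)/158 = 0.121, the half-width is 1.975 × √(0.121/30) = 0.125, and coverage is Φ((0.125 − 0.152)/0.049), about 30%. The same steps give about 89% at 25%.

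**Same cases, other rules.**

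- Half-limit substitution lowers each below-floor value by a further 0.301. The patient mean then moves by 0.057 − 0.25 × 0.301 = −0.019, or by 0.152 − 0.50 × 0.301 = +0.001. The estimates are −1.02 and −1.00.
- A censored-normal likelihood returns about −1.00 in both cases, as it should when the data are normal.

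**Both limits, if a ceiling applies.** The first share is patients below the floor and the second is healthy volunteers above the ceiling; 20 against 20, SD 0.38. The shares are again assumptions.

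| True difference (magnitude) | Shares | Set to limits | Coverage | Half-limit at floor | Dropped | Censored fit |
|---|---|---|---|---|---|---|
| 0.40 | 10%/10% | 0.37 | 0.945 | 0.395 | 0.27 | 0.39 |
| 0.40 | 30%/30% | 0.27 | 0.72 | 0.35 | 0.13 | 0.41 |
| 0.40 | 50%/50% | 0.15 | 0.00 | 0.26 | 0.04 | 0.38 |
| 1.00 | 30%/30% | 0.86 | 0.68 | 0.94 | 0.63 | 1.02 |
| 1.00 | 50%/50% | 0.70 | 0.00 | 0.85 | 0.41 | 0.99 |

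Coverage refers to values set to the limits. Power for the true 0.40 under that rule is 0.89, 0.88 and 0.83 in the three rows, against 0.90 without limits, because the SD shrinks along with the difference.

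**When non-responders are a separate mass.** Assume 40 patients, half responders with mean 5.0 and SD 0.5, half non-responders at 2.5, and a floor at 3.0. The true mean is (5.0 + 2.5)/2 = 3.75. Recording at the limit gives (5.0 + 3.0)/2 = 4.00, an error of +0.25. A censored-normal fit gives 3.29, an error of −0.46.

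**The case against.** The plan is silent; it does not say that out-of-range values are treated as exact. A reader might infer that this has been decided, but section 8.4.1 names a model and leaves laboratory handling undescribed. What stands against the plan is that the named model makes no exception, and that the results differ by rule.

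A reader might also infer that healthy responders will sit at a ceiling. The documents do not show this. The only source is a figure legend taken from a cited publication, tied to one dilution. Nothing says study samples are read at that dilution alone, and re-dilution would remove the ceiling.

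The floor is better supported, but not for every group. Section 8.3 says poor, not undetectable, and expects most other groups to respond. The statement about no antibody concerns one condition. Naive baselines are a sample-size assumption, and section 4.1 allows people to enroll after vaccination with a pre-booster baseline.

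Nor is the direction general. With a floor only, half-limit substitution nearly removes the bias at SD 0.38. That result depends on the SD and the shares, so it is a reason to fix the rule in advance, not a reason to leave it open.

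The strongest point is that a censored-normal model can do worse than recording at the limit when non-responders form a separate mass, which is the motivating case here. This stands, and it is why the censored model needs a responder analysis beside it.

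Finally, the study is exploratory, has no decision threshold and loses little power. That limits the consequence but does not remove it, because the estimate is the result that will be reported.

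**Conclusion.** The concern holds in conditional form. Section 8.4.1 gives no treatment of out-of-range titers, and the protocol's own expectations make floor values foreseeable in some groups and at baseline. If they enter at the limit, the difference is understated and the interval under-covers: from -1.00 to -0.94 (85% coverage) with 25% of patients below the floor, and to -0.85 (11%) with 50% below. Those coverages use separate group variances; a common variance gives about 89% and 30%.

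The figures rest on SD 0.38 in both groups, 120 against 40 participants, normal log titers and assumed shares. The documents give no limits or shares, so the actual size cannot be derived from them. A ceiling would add to the loss but is only a possibility. The documents do not support saying that the contrast is always biased toward no difference, or that a censored-normal model alone would solve the problem. The harm is to the estimate and its interval, much less to power. The change should be made, because it is cheap and the rule is best fixed before titers are seen.

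**What to change.** In section 8.4.1:

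1. State the lower and upper limits of quantification for S and RBD IgG, by sample type and dilution, and whether samples above the range are re-diluted.
2. Fit values below the lower limit as left-censored, and any remaining above the upper limit as right-censored, in the mixed model instead of as exact values. The brms package, already named, can do this; its stated purpose would widen beyond prior information.
3. Report the percentage censored by group and timepoint.
4. Where baseline is below the limit, enter a below-limit indicator instead of a substituted value.
5. Report the proportion above the lower limit (responders) by group, or a two-part analysis, for groups with heavy censoring.

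The cost is SAP wording and longer model fitting, with no new samples, visits or participants. The downside is dependence on an assumed tail below the floor; the responder proportion is the check on it.
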